5.3. Study Visit Instructions

The Visit Status case report form is required for each study visit and telephone contact whether or not the visit or call was actually performed. This form documents whether or not the visit took place and the reasons why if it didn't. It also serves as a reminder to update the AE Log, Concomitant Medication Log, Dose Management Log, and the Drug Dispense and Return Log, if needed.

Baseline Visit (Day 0) Instructions:

Drug randomization will occur at the Baseline visit after review of all inclusion/exclusion criteria, receipt of confirmation from the BP vendor website to proceed and the in-person BP readings meet criteria for dosage escalation and review of vital signs obtained at the site visit. After entering data into the eClinical system, the site will be given a Randomization/Enrollment ID number that will correspond to a drug kit. Record this number on the drug dispensing/return log. Dispense only Bottle 1 from the kit that has been assigned during the randomization process. The subject who meets BP criteria at the Baseline visit should be instructed to take **one capsule from Bottle 1**, twice daily (with or without food) in the morning after recording their morning blood pressure, and in the evening (approximately 12 hours after the morning dose) after recording their evening blood pressure. The subject should continue to take the study drug, unless intolerable side effects develop, until they are seen for Visit 01. Advise the subject to report any side effects and changes in medication immediately to study staff.

In case of intolerability, the dosage of study drug should be reduced until intolerability resolves or the subject is off the study drug (see Section 4 of Ops Manual). Subjects who are unable to tolerate even the lowest dosage of study drug should be encouraged to remain in the study off the study drug.

For intolerability, dosage reduction should be attempted prior to discontinuing study drug (see Section 5.4). Instructions for dosage reduction can be given either over the phone after review of the adverse events or at the corresponding in-person visit (either regularly scheduled or unscheduled visit depending on the timing of the dosage reduction). For individuals on concomitant anti-hypertensive medication with adverse events referable to hypotension, reduction in the anti-hypertensive agent should be undertaken first (see Section 5.2.7 #7 above). Resumption of titration should happen at least a week later only at or after the in-person visit (either regularly scheduled or unscheduled visit depending on the timing of the dosage escalation) and after the Investigator receives the confirmation notice to proceed from the BP vendor website and the in-person BP readings meet criteria for dosage escalation. Subjects may resume titration to 5 mg twice daily dosage (2 capsules twice daily) at the discretion of the site Investigator provided blood pressure parameters are stable and the other intolerability issues have resolved (see Section 5.5 for re-challenge directions).

Visit 01 (Day 14/ + 3 days) Instructions:

After the Investigator receives the confirmation notice from the BP vendor website to proceed and the in-person BP readings meet criteria for dosage escalation., the subject should be instructed to begin taking **two capsules twice daily from Bottle 1 no sooner than day 15**. Study drug is taken twice daily (with or without food) in the morning after recording their morning blood pressure and in the evening (approximately 12 hours after the morning dose) after recording their evening blood pressure. The subject should continue to take the study drug, unless intolerable side effects develop, until they are seen for Visit 02. Advise the subject to report any side effects or changes in medication immediately to study staff. In case of intolerability, dosage reduction should be attempted prior to discontinuing study drug (see Section 5.4 for dose reduction instruction). For individuals on concomitant anti-hypertensive medication with adverse events referable to hypotension, reduction in the anti-hypertensive agent should be undertaken first (see 5.2.7 #7 above).

Visit 02 (Day 28 /+ 3 days) Instructions:

After the Investigator receives the confirmation notice from the BP vendor website to proceed and the in-person BP readings meet criteria for dosage escalation., the subject should be instructed to continue taking **two capsules twice daily (unless a dosage reduction has taken place)**. Subjects will be provided with 6 months study drug kits containing the remaining 5 one-month supply bottles. Study drug is taken **2 capsules twice daily** (with or without food) in the morning and in the evening, approximately 12 hours after their morning dose. The subject should continue to take the study drug, unless side effects develop, until they are seen for Visit 03. Subjects should be instructed to use all of the capsules in one bottle before opening the next bottle of study drug. Advise the subject to report any side effects or changes in medication immediately to study staff. In case of intolerability, dosage reductions should be attempted prior to discontinuing study drug. For individuals on concomitant anti-hypertensive medication with adverse events referable to hypotension, reduction in the anti-hypertensive agent should be undertaken first (see Section 5.2.7 #7). Instructions for dosage reduction and re-challenges are per the Section 5.3.

5.4 Study Drug Reductions

Dosage reductions can occur at any time during the study. Random dose adjustments may be done in both study groups (active or placebo) at the direction of the Biostatistician at the University of Rochester in order to preserve the study blinding. In case of intolerability, dosage reduction should be attempted prior to discontinuing study drug. Instructions for dosage reduction may be given either over the phone after review of the adverse events or at the corresponding in-person visit (either regularly scheduled or unscheduled visit depending on the timing of the dosage reduction). See below for dosage reduction directions. **For individuals on concomitant anti-hypertensive medication with adverse events referable to hypotension, reduction in the anti-hypertensive agent should be undertaken first** (see 5.2.7 #7 above).

Subjects will reduce their dosage in a blinded fashion by 1 capsule (equivalent to 2.5 mg of Isradipine IR or placebo) each week. Dosage reduction should start by withdrawing a capsule from AM dose if on 10mg daily dosing (2 capsules twice daily). Subjects unable to tolerate 7.5mg dosage (one capsule in AM and two capsules in the evening daily) after a week will be instructed to reduce the dosage further to one capsule twice daily (equivalent to 5 mg Isradipine IR or placebo daily). Subjects unable to tolerate 5 mg daily dosage after a week will be instructed to reduce the dosage further to one capsule once daily taken in PM (equivalent to 2.5 mg Isradipine IR or placebo daily). Subjects unable to tolerate 2.5 mg daily dose will be taken off the study drug. In accordance with the intent-to-treat principle these subjects will be encouraged to remain in the study and every attempt will be made to continue to follow them and obtain the primary outcome data.

All study drug reductions must be called to the CTCC.

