5.5 Study Drug Re-challenge (Resumption of Titration)

Titration should be completed by Visit 03, Month 3. Visit 03 will be the formal beginning of the maintenance phase of the study.

Resumption of titration can occur through the titration period at the discretion of the Investigator. Re-challenges following dosage reductions may occur at any time during the study (titration or maintenance).

Subjects may resume titration to 5 mg twice daily dosage (2 capsules twice daily) at the discretion of the site Investigator provided the in-person BP readings meet criteria for dosage escalation and other tolerability issues have resolved. The dosage should be increased by one capsule twice daily (as per initial titration every two weeks) until the subject is on 2 capsules twice daily or intolerability recurs. At the discretion of the Investigator titration can be done in increments of 2.5 mg (1 capsule) always adding the evening dose first. Subjects that are unable to tolerate a dosage increase will be reduced to the highest tolerated dosage [either 7.5 mg (2.5 mg in the AM and 5 mg in the evening, 5 mg

(2.5 mg twice daily) or 2.5 mg daily (one capsule in the PM) dosage] and enter the maintenance phase of the study. Subjects unable to tolerate 2.5 mg daily (one capsule in the PM) dosage will be taken off the study drug and will be encouraged to remain in the study.

All attempts at re-titration of study drug must be called to the CTCC.

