Assess Need for symptomatic therapy (completed only if subject has not reached need for symptomatic therapy).

Once the subject initiated symptomatic therapy, UPDRS Part III assessment should be completed in the defined medications OFF state (approximately 12 hours after the last dose of symptomatic therapy) **and** in medications ON state (based on the subject/ investigator defined BEST ON, approximately 1 hour after dose of symptomatic therapy). Subjects should be instructed NOT to take their PD medications at home on the morning of the study visit. Subjects should be instructed to bring their PD medication to the study visit. Medication should be taken after completion of UPDRS OFF exam. UPDRS Parts 1 and 2 are to be completed in the ON state. Once a subject starts symptomatic therapy, the ON and OFF assessments should be completed for all PD medications including dopamine agonists, MAO inhibitors, or any other dopaminergic therapies.

- Modified Hoehn & Yahr Scale
- Modified Schwab & England Activities of Daily Living
- Adherence Assessments (see Section 6.3.13)
- Dispense Study Drug (Visits 04, 07 and 09 Only)
- Dose Management Log
- Drug Dispensing/Return Log (pill counts)
- Adverse Event Log

Plasma PK sample will be collected at Visit 03 (Month 3 +/- 7 days) and Visit 04 (Month 6 +/- 7 days)

- Visit should be scheduled in AM as close to 12 hours **post evening dose of the study drug**
- Subjects should be instructed NOT to take their study drug at home on the morning of the study visit.
- Time of the last dose of the study drug should be documented
- Plasma PK sample should be collected (samples should be collected as close to 12 hours post dose as possible) and time of sample collection should be documented
- The subject should take morning dose of the study drug during the visit

- Repeat PK sample should be collected 2-3 hours post dose
- Time of the last dose of the study drug should be documented
- Time of all samples collection should be documented
- **Plasma PK sample will be collected at Visit 04 (Month 6 +/- 7 days).**
- Visit should be scheduled to **occur within 4-8 hours post morning dose of the study drug**
- Subjects should be instructed to take their study drug at home on the morning of the study visit
- Time of the last dose of the study drug should be documented
- Time of the samples collection should be documented

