- V. An interim tolerability analysis will be performed after the first 60 subjects complete titration period of the study (Visit 03) as discussed in section 8.C.

B. *Procedure.*

All subjects known to have received study treatment will be included in the safety analysis.

All adverse events and abnormal laboratory values results will be listed by treatment and be identified by subject and site. They will also be tabulated by treatment group, severity and perceived relationship to study medication. Fisher's exact test will be used to compare each active treatment group to the placebo group with regard to the proportion of subjects experiencing a particular adverse event. Separate analyses will be performed excluding mild events and those categorized as unrelated to study medication. In all comparative analyses, events occurring after Baseline Visit will not be counted if the subject experienced the event at the Baseline Visit, unless the severity increases.

A similar approach will be adopted to compare out-of-range laboratory values between groups.

The following measures of the effect of the study drug on vital signs, specifically on orthostatic blood pressure will be analyzed:

- Changes in vital signs recorded at each visit.
- The proportions of subjects who develop orthostatic hypotension as defined by a drop in systolic blood pressure of greater than or equal 20 mm Hg and a drop in diastolic blood pressure of greater than or equal to 10 mm Hg when going from a supine to a standing position.
- The proportions of subjects who develop symptomatic orthostatic hypotension, defined as orthostatic blood pressure changes, as defined previously, associated with presence of positional dizziness or other symptoms.

Comparisons of the active treatment group with the placebo will be made using by Fisher's exact tests

C. Analysis by Subgroups, Including Race and Gender.

Primary safety and tolerability data will be tabulated separately for selected subgroups of the population defined by baseline characteristics, including gender and race/ethnicity.

6. Exploratory Analysis

An analysis of the correlation between clinical efficacy measures and serum PK concentrations will be performed. The analysis will be based on correlation of the change of the efficacy measures and serum concentration of isradipine measured as AUC 0-12 hour based on the sparse PK profile collected during the study.

7. Power and Sample Size Considerations

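### The exploratory exposure-efficacy correlation takes exposure from the morning dosing interval, which understates daily exposure at 7.5 mg/day and at 2.5 mg evening-only

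*Protocol*

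**What the plan says.** **Exposure metric.** Protocol 8.2.2 (Exploratory analysis) and SAP 6 both define exposure for the correlation with efficacy change as "serum concentration of isradipine measured as AUC 0-12 hour based on the sparse PK profile collected during the study". Neither says how the AUC is derived, and neither has a rule for subjects on a reduced dose.

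**Sampling.** Protocol 6.2.4 gives three samples, and 6.3.10 confirms the two post-dose windows.
- Visit 03, trough: "Visit should be scheduled in AM as close to 12 hours" after the evening dose as possible.
- Visit 03, post-dose: "The subject should take morning dose of the study drug during the visit", and then "Repeat PK sample should be collected 2-3 hours post dose".
- Visit 04: one sample 4-8 hours after a morning dose taken at home.

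**Reduced regimens.** Protocol 5.4 takes the first capsule from the morning dose. It describes the next group to reduce as "Subjects unable to tolerate 7.5mg dosage (one capsule in AM and two capsules in the evening daily) after a week", which makes 7.5 mg/day 2.5 mg in the morning plus 5 mg in the evening. The 5 mg/day step is one capsule twice daily. The lowest step, restated in 5.5, is "2.5 mg daily (one capsule in the PM) dosage". Rule 8 in 5.2.7 recognises this once-daily exception.

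**Scope.** The interim PK analysis (Protocol 8.1, SAP 8.C) is limited to subjects who reached 10 mg/day. The exploratory correlation has no such limit.

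**The concern.** The sampled interval is the one after the morning dose. Its AUC equals half the daily exposure only if the morning and evening doses are the same. At 7.5 mg/day it covers the smaller half of the day. At 2.5 mg evening-only it covers only the tail of the previous evening's dose.

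The planned correlation would then carry a downward error in exposure for these two regimens. The error has a known direction, and a larger sample does not remove it. At stake is how well one exploratory analysis describes the relation between exposure and response.

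There is also a practical gap. The 6.2.4 instructions presuppose a morning dose at both visits, and the evening-only regimen has none. As written, only the trough can be drawn in those subjects.

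**Working it through.** **Inputs**
- Expected AUC 0-12 at 5 mg twice daily: 13.9 ± 6.1 (Protocol 8.1; printed in ng/ml, read as ng·h/ml).
- Cmax 5.5 and Cmin 0.4 ng/ml at the same dose (Protocol 2.1; 2.3 gives Cmax as 5.53).
- Half-life of the plain formulation: 9.5 h after the first dose and 13.1 h at steady state (Table 1). Peak at about 1.5 h (Protocol 2.2).
- Assumed: linear kinetics, so contributions of separate doses add.

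The plan's 13.9 comes from a cited study and cannot be reproduced, because the documents hold no concentration-time data. A bi-exponential curve fitted to Cmax, Cmin and AUC with terminal half-lives of 9.5-25.1 h returns 14.2-14.9. The three figures are therefore roughly compatible, though the fitted peak is early (0.6-0.7 h).

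**Step 1: evening dose carried into the morning interval, at full dose**

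With λ = ln 2 / half-life and q = exp(-12λ), the trough of 0.4 decays over the next 12 h with area T = 0.4(1-q)/λ. The part due to evening doses is S = T/(1+q).
- Half-life 2.8 h (fall from 5.53 at 1.5 h to 0.4 at 12 h): q = 0.051, T = 1.53, S = 1.46.
- Half-life 13.1 h: q = 0.530, T = 3.55, S = 2.32.

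**Step 2: morning-interval AUC by regimen**

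Let a and p be the morning and evening doses in units of 5 mg. Morning AUC = a(13.9 - S) + pS.

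| Regimen | Morning AUC 0-12 | Relative to full dose | True relative daily exposure | Error |
|---|---|---|---|---|
| 10 mg (a = 1, p = 1) | 13.9 | 1.00 | 1.00 | none |
| 7.5 mg (0.5, 1) | 6.95 + S/2 = 7.68-8.11 | 0.55-0.58 | 0.75 | 22-26% low |
| 5 mg (0.5, 0.5) | 6.95 | 0.50 | 0.50 | none |
| 2.5 mg evening (0, 0.5) | S/2 = 0.73-1.16 | 0.05-0.08 | 0.25 | 67-79% low |

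A 7.5 mg/day subject reads 7.68/6.95 to 8.11/6.95, that is 10-17% above a 5 mg/day subject instead of 50%.

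**Step 3: stress test on the kinetics**

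Suppose a one-compartment curve with the Table 1 mean half-lives governed the whole interval. With instantaneous absorption the share of a dose's AUC falling in its own half-day is g = 1/(1+q), or 0.706 and 0.654. The 7.5 mg reading relative to 5 mg is then 2 - g = 1.29 and 1.35. Allowing for absorption with a peak at 1.5 h, it is 0.65-0.68 of full dose, so about 30-36% above 5 mg. This curve implies a peak-to-trough ratio near 2, against the stated 5.5/0.4, about 14.

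**Step 4: effect on the correlation**

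Suppose efficacy change is linear in daily exposure, with between-subject CV 6.1/13.9 = 0.439, so 1 + CV² = 1.193. Let t and m be a subject's true and measured relative exposure. Then

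Cov = 1.193·E[tm] - E[t]E[m], and Var(m) = 1.193·E[m²] - (E[m])²; Var(t) has the same form.

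The slope is multiplied by Cov/Var(m), and the correlation by Cov/√(Var(t)·Var(m)). The shares and mixes below are assumptions.
- 5% on the two regimens, three-quarters of them on 7.5 mg, S = 2.32: Cov = 0.1982, Var(m) = 0.2017, Var(t) = 0.1962. Slope 1.8% low, correlation 0.4% lower.
- 28%, split equally, S = 1.46: Cov = 0.2380, Var(m) = 0.2626, Var(t) = 0.2234. Slope 9.3% low, correlation 1.7% lower.

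**The case against.** **Consequence.** The analysis is exploratory, with no alpha, threshold or decision attached, and the correlation barely moves. This stands and sets the priority low.

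**Share affected.** The Phase II figure of 7/26 = 27% at 10 mg might be read as the share affected. It counts any reduction or suspension over 52 weeks on the CR formulation, including transient ones. The share on these two regimens at Months 3 to 6 should be lower, so 28% is an upper bound for illustration. This stands.

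**Model dependence.** A reader might infer that 7.5 mg and 5 mg subjects become indistinguishable. The documents do not support that. The reading is 10-17% higher on the stated trough and AUC, and more under long half-lives. The 2.8 h half-life is also not coherent as a single curve: decay from 5.53 to 0.4 over 10.5 h alone gives about 20.6 ng·h/ml, above 13.9. Both approaches still fall well short of the true 50%.

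**Low end of exposure.** Reduced-dose subjects are not its only source. With 13.9 ± 6.1, about 13-16% of full-dose subjects already lie below 7.9. This stands.

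**Extra dose.** One might read 6.2.4 as ordering an additional morning dose for evening-only subjects. That is strained, since 5.2.7 rule 8 acknowledges once-daily dosing. What remains is a missing sampling instruction.

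**Choice of metric.** The protocol's rationale also invokes a floor concentration, so nothing in it proves that 24-hour AUC drives efficacy. That is fair, but it does not rescue a morning-only area as a summary of unequal regimens.

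**Existing cover.** Protocol 8.2.1 plans an exploratory analysis by achieved final dosage, which separates the dose levels. It does not correct the PK metric. Dose times and the Dose Management Log could support modelling of dose history, but neither document says they will be used.

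**Conclusion.** The point holds as a minor one, confined to the exploratory exposure-efficacy correlation. AUC 0-12 from morning-dose samples is a sound half-day summary at 10 and 5 mg/day. It understates exposure by 22-26% at 7.5 mg/day and by 67-79% at 2.5 mg evening-only, given linear kinetics and the protocol's Cmin and AUC. Under the less well-fitting one-compartment alternative, 7.5 mg would read about 30-36% above 5 mg, still short of 50%.

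The error is large for the subjects concerned and small overall. For assumed shares of 5-28% the slope is about 2-9% too low and the correlation about 0.4-2% lower. These figures describe an ideal morning AUC, not the noisier estimate that three samples would give.

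A reader might infer that the trial's main results or its PK go/no-go check are compromised. They are not: the primary analysis and sample size do not use PK data, and the interim check includes only 10 mg/day subjects.

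**What to change.** **SAP 6 and Protocol 8.2.2.** Replace AUC 0-12 by 24-hour exposure (AUC 0-24 or average concentration). Predict it from the sparse samples, using each subject's actual morning and evening doses from the Dose Management Log and the documented dose and sample times. State how a dose change between Visits 03 and 04 is handled, since the two visits are three months apart and reductions are allowed at any time.

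Under linear kinetics the expected AUC 0-24 is 2 × 13.9 × (daily dose/10): 27.8, 20.9, 13.9 and 7.0 ng·h/ml at 10, 7.5, 5 and 2.5 mg/day. It is proportional to daily dose however the dose is split.

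The cost is a sentence or two of text and a small amount of extra PK modelling on data already collected. Where only the trough exists, the prediction will lean more heavily on the model, and the SAP should say so.

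**Protocol 6.2.4 against 5.4/5.5.** The morning-dose sampling instructions at Visits 03 and 04 and the evening-only regimen must be reconciled. No dose or regimen is proposed here. This wording change helps only for visits still to come; the SAP change works on existing data.

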5.5 Study Drug Re-challenge (Resumption of Titration)

Titration should be completed by Visit 03, Month 3. Visit 03 will be the formal beginning of the maintenance phase of the study.

Resumption of titration can occur through the titration period at the discretion of the Investigator. Re-challenges following dosage reductions may occur at any time during the study (titration or maintenance).

Subjects may resume titration to 5 mg twice daily dosage (2 capsules twice daily) at the discretion of the site Investigator provided the in-person BP readings meet criteria for dosage escalation and other tolerability issues have resolved. The dosage should be increased by one capsule twice daily (as per initial titration every two weeks) until the subject is on 2 capsules twice daily or intolerability recurs. At the discretion of the Investigator titration can be done in increments of 2.5 mg (1 capsule) always adding the evening dose first. Subjects that are unable to tolerate a dosage increase will be reduced to the highest tolerated dosage [either 7.5 mg (2.5 mg in the AM and 5 mg in the evening, 5 mg

(2.5 mg twice daily) or 2.5 mg daily (one capsule in the PM) dosage] and enter the maintenance phase of the study. Subjects unable to tolerate 2.5 mg daily (one capsule in the PM) dosage will be taken off the study drug and will be encouraged to remain in the study.

All attempts at re-titration of study drug must be called to the CTCC.

